### **Study Title:**

A 2-arm, open label, prefatory study to explore changes in nasal mucociliary clearance between smokers and never smokers and to standardize nasal scraping procedure

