**Clinical Study Protocol** 

Confidential

P1-CMS-01-US

Final 2.0 Amendment 1.0, 22-May-2017

Page 36 of 106

Related to PMI\_RD\_WKI\_000759

( $16\pm 6 \text{ min}$ ; p = 0.005 versus non-smokers' and p = 0.003 versus immediately after smoking), (Proença et al., 2011). The alterations of the STT value over time are not fully clear, as was demonstrated in the above study where no baseline measurement was reported. Therefore, based on this, the need for the present prefatory study and its proposed design is justified. In order to better understand the difference in STT over time between smokers and never smokers, a never smoker group is added to the study design.

Additionally, samples from nasal scrapings using two methods will be collected during the study from smokers and never smokers. These two methods will be used in this prefatory study to identify and standardize the optimal one which results in the highest quantity and quality of ribonucleic acid (RNA) for further transcriptomics analysis. The use of multi-omics have been used to elucidate mechanistic pathways which are impacted by cigarette smoking. The transcriptome of multiple tissues are known to be altered due to cigarette smoke exposure. Through targeted transcriptomic analysis from nasal sampling, increased expression and identification of antioxidant and xenobiotic genes as well as a wide spectrum of inflammation-related genes can be characterized. (Martin, Talikka, Hoeng, & Peitsch, 2015; Phillips et al., 2016; Titz et al., 2016).

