**Clinical Study Protocol** 

Confidential

P1-CMS-01-US

Final 2.0 Amendment 1.0, 22-May-2017

Page 41 of 106

Related to PMI\_RD\_WKI\_000759

test performed immediately after smoking (5-10 minutes post T0). T0 will be defined as the start of cigarette smoking for smokers (time point of first product use during study day). T0 should be the same for all smokers within an acceptable time window of 1 hour. Never smokers will also have the STT test performed in the morning at 8 am  $\pm$  30 minutes (designated T0 $\pm$  30 minutes). All study participants (smokers and never smokers) will then have the STT test performed until 4h30 min), 8h (may be performed until 8h30 min), and 12h (may be performed until 12h30 min) post T0, ensuring at least approximately 4 hours between the beginning of each STT test. The participant will be asked to confirm he can no longer feel the sweet taste. Study participants will drink a glass of water (approximately 240 mL) before STT tests are performed.

Samples for plasma nicotine assessment will be collected at approximately the same time points that STT test is performed at  $T_0$ , 4h (may be performed until 4h30 min), 8h (may be performed until 8h30 min), and 12h (may be performed until 12h30 min) post  $T_0$ .

Nasal scraping of the inferior turbinate of both nostrils will be performed on all 14 study participants at the end of Visit 3, after all other clinic assessments, except the brief physical examination which will be done after the nasal scraping:

- For 4 study participants, the nasal scraping (left nostril with method 1, right with method 2) will be performed and samples collected for subsequent histological assessment.
- For the 10 remaining study participants, 5 will undergo nasal scraping using method 1, and 5 using method 2. For all 10 study participants, cells from one nostril will be added into one buffer, cells from the other nostril into a second buffer. Samples will be collected for subsequent RNA quantity and quality analysis.

Full procedure is described in the "Method establishment to obtain human nasal epithelial sample using the Rhino-probe".

Upon conclusion of all clinic assessments, at the time of discharge on Visit 3, the Principal Investigator or designee will perform a brief physical examination on the study participant.

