# 7.2.8.8 Nasal scraping, sical assessment and biological specimen collections for further analysis

See Appendix A - Schedule of Events for the timepoints of assessment.

Nasal scraping of the inferior turbinate of both nostrils will be performed on all 14 study participants as described in the separate document "Method establishment to obtain human nasal epithelial sample using the Rhino-probe".

For 4 study participants, nasal scraping (left nostril with method 1, right with method 2) will be performed and cell samples will be collected, processed, appropriately labeled and shipped by the study site as per the "Method establishment to obtain human nasal epithelial sample using the Rhino-probe" to the appropriate laboratory for further histological assessment.

For the 10 remaining study participants, 5 will undergo nasal scraping using method 1, and 5 using method 2. For all 10 study participants, cell sample from one nostril will be added into one buffer and cell sample from the other nostril into a second buffer. Samples will be collected, processed, appropriately labeled and shipped by the study site as per the "Method establishment to obtain human nasal epithelial sample using the Rhino-probe" to the appropriate laboratory for subsequent RNA quantity and quality analysis.

RNA quantity and quality will be assessed as per the Sponsor internal laboratory SOPs. RNA from the nasal sample will be extracted. Then a quantification step will occur using a Nanodrop 1000 instrument (TermoFisher scientific).

The quality will be assessed by using a Bioanlayzer 2100 (Agilent Technologies): the Bioanalyzer delivers a mark from 1 to 10 (10 is the best) to give an idea of the quality and integrity of the RNA (RIN value stands for RNA integrity Number).

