# **12.2** Determination of Sample Size and Power Consideration

This is an exploratory study. This study will include 14 study participants: 7 cigarette smokers and 7 never smokers. No formal powering has occurred. However, with an expected standard deviation of 2.5 minutes, a difference in STT of 3.75 minutes can be detected.

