#### 5.5 Statistical analysis

All quantitative variables will be summarized through descriptive statistics namely mean, median, standard deviation, quartiles (Q1 and Q3) and minimum and maximum values. Qualitative variables will be summarized through number (n) and frequency distribution (%).

All descriptive analyses will be performed by smoker and never smoker group.

Statistical tests will be two-tailed considering a significance level of 5%.

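### Participants are split between histology, scraping method 1 and scraping method 2 by count only, with no allocation rule and no balance on smoking group, so the 5 versus 5 RNA comparison is open to confounding

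*Protocol*

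**What the plan says.** The synopsis (Study Design), Protocol 4.1 and Protocol 7.2.8.8 divide the 14 participants by number. Four go to histology, each scraped with method 1 on the left and method 2 on the right. For the rest, "For the 10 remaining study participants, 5 will undergo nasal scraping using method 1, and 5 using method 2". In each of those ten, "cell sample from one nostril will be added into one buffer and cell sample from the other nostril into a second buffer".

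No section of the protocol or SAP says how a participant comes to be among the four, the five or the other five. There is no randomisation, sequence, enrolment-order rule, stratification by smoking group or named decision-maker. The synopsis, 4.1 and 9.2 refer to a separate Rhino-probe method document for the full procedure. It is not in the review set.

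The purpose is comparative. Protocol 2.1 and 4.2 say the two methods are used to "identify and standardize the optimal one which results in the highest quantity and quality of ribonucleic acid (RNA"). Standardising the procedure is secondary objective 1 (3.2).

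The planned analysis is descriptive. Protocol 12.1 summarises RNA concentration and RIN by method, with a 95% CI for each. SAP 5.5.4.1 summarises RNA by smoking group and Table A 9 by method, and neither shows a CI. No document plans a method difference or a test.

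**The concern.** Smoking status cannot be assigned; scraping method can, and it is the one between-person factor the study assigns. With five participants per method and a choice that will follow the observed means, whatever decides who gets which method enters the comparison directly. Three routes are open:

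- **Selection.** The title describes "A 2-arm, open label, prefatory study". Appendix A schedules nasal exams at Visits 1 and 2, and 7.2.8.7 places saccharin under direct vision on the inferior turbinate, the structure later scraped. Site staff have thus seen that tissue before a method is used.
- **Running order.** Nothing prevents all method 1 cases being done first and all method 2 cases afterwards, so operator learning would favour the later method.
- **Smoking group.** Nothing keeps smokers and never smokers balanced between the methods.

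At stake is the choice of method for later transcriptomics. The allocation could not be checked afterwards either: none of the SAP's 15 listings covers RNA or scraping, and Table A 9 shows no buffer, operator or order.

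**Working it through.** **1. The plan's own figure.** Protocol 12.2 says "This study will include 14 study participants: 7 cigarette smokers and 7 never smokers" and "with an expected standard deviation of 2.5 minutes, a difference in STT of 3.75 minutes can be detected". SAP 5.5 adds "Statistical tests will be two-tailed considering a significance level of 5" per cent. Power is not stated ("No formal powering has occurred"), so I assume 80%. By the normal approximation, n per group = 2 × (1.960 + 0.842)² × (2.5/3.75)² = 6.98, which rounds up to 7 and reproduces the 14. That figure concerns STT in smokers and never smokers. No size or precision figure is given for method 1 against method 2.

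**2. Precision at 5 versus 5, in SD units of the RNA outcome.** The standard error of a difference is √(2/5) = 0.63 SD. The 95% half-width with 8 degrees of freedom is 2.306 × 0.63 = 1.46 SD.

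**3. Freedom left by the text.** There are 14!/(4! 5! 5!) = 252,252 ways to fill 4/5/5, and the documents do not say how one is chosen.

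**4. Selection (assumed inputs).** Suppose the methods are equal, impression correlates r with yield, and the five better-looking noses all get one method. In 200,000 simulated sets of ten standard normal scores, the mean of the upper five minus the mean of the lower five was 1.48 SD, so bias = 1.48 × r.

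| r | Bias (SD) | Favoured method has the higher mean |
|---|---|---|
| 0.2 | 0.30 | 68% |
| 0.3 | 0.44 | 77% |
| 0.5 | 0.74 | 90% |

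With r = 0 the last column is 50%.

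**5. Running order (assumed drift).** If yield rises linearly by 1 SD from case 1 to case 10 and the methods are run in sequence, mean position moves from 3 to 8. The later method gains (8 − 3)/9 = 0.56 SD.

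**6. Smoking group.** Let s1 and s2 be the smokers under methods 1 and 2, and δ the smoker versus never-smoker difference in the RNA outcome, in SD (not given, so assumed). Bias = δ × (s1 − s2)/5.

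- As written, s1 = 5, s2 = 0 with 2 smokers in histology is allowed: bias = δ, with method and smoking group fully confounded.
- A simple unstratified random list gives a smoker difference of 2 or more in 35.9% of draws and 3 or more in 12.6% (exact count over the 3,432 placements of 7 smokers).
- A list stratified as smokers 2/3/2 and never smokers 2/2/3 (histology/method 1/method 2) fixes the split at 3 versus 2: bias = 0.2 × δ. It still leaves (7!/(2! 3! 2!))² = 210² = 44,100 possible lists.

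**The case against.** The strongest reply is that the rule may exist in the Rhino-probe document, to which the protocol sends the full procedure. This stands as a limit: the finding is only that the protocol and SAP state no rule.

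The illustration in step 4 also assumes perfect sorting, on correlations with no basis in the documents. No reason is given why staff would favour either method. Exclusion criteria 4 and 12 narrow the range of nasal anatomy. At r = 0.2 to 0.3 the bias is below one standard error. All of this is fair: the figures show what the gap allows, not what will happen. It does not remove the gap, because a choice made on observed means can be decided by a shift of that size.

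A reader might infer more than the documents support:

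- **That staff will pick methods by impression, or that the nasal examiner does the scraping.** Neither is stated; the first is an inference from silence.
- **That free choice of nostril for each buffer biases method 1 against method 2.** It cannot. Each RNA participant has one method in both nostrils and fills both buffers, so buffer is balanced within person. Only a buffer comparison could suffer, and none is planned.
- **That methods are chosen for the histology participants.** They receive both, with side fixed. What is open is who enters that group, and so who remains for RNA.
- **That a planned confidence interval loses its coverage.** No interval for the method difference is planned.
- **That RNA scoring is exposed.** Quantity and RIN are instrument-read (7.2.8.8). The exposure lies in who gets which method and in the scraping itself.

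**Conclusion.** The point holds on the documents supplied. The one assignable between-person factor is allocated by count alone, without a random or other rule and without balance on smoking group, although its comparison is meant to select a method. Selection, running order and smoking group can each be confounded with method, and 5 smokers against 0 is permitted.

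The size of any bias is unknown. The illustrations give about 0.3 to 0.7 SD for selection (r from 0.2 to 0.5, complete sorting), 0.56 SD for a 1 SD drift run in sequence, and up to the full smoking effect for group imbalance. All rest on assumed inputs.

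The consequence is limited to a secondary, descriptive objective of an exploratory study. The STT comparison is untouched, because its groups are defined by smoking status. The change is worth making because it is almost free.

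**What to change.** In the synopsis, 4.1 and 7.2.8.8, state that a random list prepared by the CRO before the first Visit 2, stratified by smoking group, assigns each participant to histology, method 1 or method 2. One workable split is smokers 2 histology/3 method 1/2 method 2 and never smokers 2/2/3. A further random draw can settle which method receives the third smoker. Assignments go in pre-prepared sealed envelopes, opened after the 12 h STT test. That test can end as late as about 22:00 (08:30 + 12 h 30 min + 60 min), and envelopes avoid evening data-management cover. If the Rhino-probe document already contains such a rule, cite it instead.

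Randomising nostril to buffer is optional and matters only if buffers are to be compared.

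Record method, nostril, buffer, operator and scraping order in the eCRF, and create an RNA listing in the SAP. At the same time, reconcile the RNA summaries: by method in Protocol 12.1, by smoking group in SAP 5.5.4.1, and Table A 9's RNA row for the four participants whose samples go to histology.

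Cost: a 14-line list, 14 envelopes, a paragraph repeated in three places, a few eCRF fields and one listing. There are no extra participants, visits or procedures, and 4/5/5 is kept. The small downside is that the operator must be ready to use either method for any participant.

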## **Confidentiality Statement**

Data and information contained in this document are considered to constitute trade secrets and confidential commercial information, and the legal protections provided to such trade secrets and confidential information are hereby claimed under the provisions of applicable law. No part of this document may be publicly disclosed without the written consent of Philip Morris Products S.A.

Philip Morris Products SA

Clinical Study Protocol

Confidential

P1-CMS-01-US

Final 2.0 Amendment 1.0, 22-May-2017

Page 42 of 106

Related to PMI\_RD\_WKI\_000759

Any non-serious AE that is ongoing during the Safety Follow-Up Period will be actively followed-up by the Principal Investigator or designee during that period until it has been resolved, stabilized (i.e., no worsening of the condition), an acceptable explanation has been found (e.g., a chronic condition) or lost to follow up.

At the end of the Safety Follow-Up Period, all ongoing non-serious AEs will be documented as "ongoing" and no follow-up information will be sought for on them anymore by the Principal Investigator or designee. At that point, the Investigator will assess whether the subject should be referred to his/her General Practicioner to have their ongoing AEs addressed accordingly.

All SAEs will be followed up by the Investigator or designee, despite their continuation after the end of the Safety Follow-Up Period, until their resolution, stabilization (i.e., no worsening of the condition), or an acceptable explanation has been found (e.g., a chronic condition).

Subjects who are discontinued from the study because of an AE will undergo the early termination procedures as soon as practical after the day of discontinuation and will enter the period of safety follow-up.

The end of the study for a study participant is defined as the date of discharge on Visit 3 plus one day of Safety Follow-Up Period or the date of early termination of the study participant plus one day of Safety Follow-Up Period.

The end of the entire study is defined as the end of the Safety Follow-Up Period of the last study participant.

## Figure 1 Study Flow Chart

# 4.2 Rationale for Study Design

Several authors have reported a decreased NMC in smokers versus non smokers and even passive smokers (Stanley et al., 1986, Habesoglu 2012, Utiyama et al., 2016). Moderate and heavy smokers show higher STT results than light smokers and non-smokers (Xavier et al., 2013). Decreased mucociliary function was observed in people with moderate and heavy cigarette consumption (Proença et al. 2012). Smoking cessation appears to contribute favorably to mucociliary clearance (Ramos et al. 2011).

Proença et al. 2011 have studied the acute and short term effects of smoking on nasal mucociliary clearance in current smokers using the STT test immediately after smoking and 8 hours after the last cigarette.

**Clinical Study Protocol** 

Confidential

P1-CMS-01-US

Final 2.0 Amendment 1.0, 22-May-2017

Page 44 of 106

Related to PMI\_RD\_WKI\_000759

When compared to STT in non-smokers' ( $10\pm4$  min; mean $\pm$ standard deviation), smokers presented similar STT immediately after smoking ( $11\pm6$  min; p = 0.87) and slower STT 8 hours after smoking ( $16\pm6$  min; p = 0.005 versus non-smokers' and p = 0.003 versus immediately after smoking) (Proença et al., 2011). The alterations of the STT values over time is not fully clear as in the above study no baseline measurement has been reported and which establishes the need for the present prefatory study and justifies its proposed design. In order to better understand the difference in STT over time between smokers and never smokers, a never smoker group is added to the study design.

Additionally, samples from nasal scrapings using two methods will be collected during the study from smokers and never smokers. These two methods will be used in this prefatory study to identify and standardize the optimal one which results in the highest quantity and quality of ribonucleic acid (RNA) for further transcriptomics analysis. The use of multi-omics have been used to elucidate mechanistic pathways which are impacted by cigarette smoking. The transcriptome of multiple tissues are known to be altered due to cigarette smoke exposure. Through targeted transcriptomic analysis from nasal sampling, increased expression and identification of antioxidant and xenobiotic genes as well as a wide spectrum of inflammation-related genes can be characterized. (Martin, Talikka, Hoeng, & Peitsch, 2015; Phillips et al., 2016; Titz et al., 2016).

It was decided to focus the present study on a male population only to minimize the variability between genders.

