# **12** PLANNED STATISTICAL METHODS

# **12.1** General Considerations

Full details of the statistical analysis will be given in a Statistical Analysis Plan (SAP). Any changes to the planned statistical methods will be documented in the Clinical Study Report. The statistical evaluation will be performed using SAS®, version 9.2 or later.

STT for each time point will be summarized by smoker and never smoker group using the descriptive statistics: mean, minimum, maximum, median, quartiles, standard deviation (SD) and 95% confidence interval (CI).

The plasma nicotine levels for each time point will be summarized by smoker and never smoker group using the descriptive statistics mean, minimum, maximum, median, quartiles, standard deviation (SD) and 95% confidence interval (CI).. The relationship between plasma nicotine levels and STT at each time point will be evaluated by spearman correlation as well as graphical presentation of these endpoints by time point and smoker and never smoker group.

An overall summary of AEs will be presented by smoker and never smoker group showing the number of events and percent of study participants who experienced AEs, SAEs, severe AEs and AEs leading to study discontinuation.

RNA concentration will be summarized by method using descriptive statistics: mean, minimum, maximum, median, quartiles, standard deviation (SD) and 95% confidence interval (CI)..

RNA RIN will be summarized by method using descriptive statistics: mean, minimum, maximum, median, quartiles, standard deviation (SD) and 95% confidence interval (CI).

A summary of AEs by System Organ Class (SOC) and Preferred Term (PT) by smoker and never smoker group will be presented.

Vital signs will be summarized by smoker and never smoker group using descriptive statistics: mean, minimum, maximum, median, quartiles, standard deviation (SD) and 95% confidence interval (CI)..

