12.1.2 Significance Level for Inferential Analysis

This study has no formal pre-specified hypotheses associated with the study objectives. However, 95% CI will accompany all effect estimates.

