### Table A 9 – Nasal scraping at visit 3 – FAS population

	Total (n=xx)
Method, n (%) Left nostril (method 1) Right nostril (method 2) Total	
Only method 1 (5 subjects) RNA N Mean Median Standard Deviation Q1 Q3 Minimum Maximum	
Only method 2 (5 subjects) RNA N Mean Median Standard Deviation Q1 Q3 Minimum Maximum	
Method 1 or 2 (10 subjects) RNA N Mean Median Standard Deviation Q1 Q3 Minimum Maximum	
Method 1 and 2 (4 subjects) RNA N Mean Median Standard Deviation Q1 Q3 Minimum Maximum	

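### Choosing a nasal scraping method on RNA: no between-method estimate is planned, and the SAP output does not separate quantity from quality

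*Protocol*

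**What the plan says.** The aim is in protocol 2.1 and again in 4.2: the two methods serve to "identify and standardize the optimal one which results in the highest quantity and quality of ribonucleic acid (RNA", for use in later transcriptomic work. It sits behind secondary objective 1, the standardisation of nasal scraping.

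The RNA data are described in protocol 4.1: "For the 10 remaining study participants, 5 will undergo nasal scraping using method 1, and 5 using method 2". These are different people, so the method comparison is between participants. Each gives two samples: "cells from one nostril will be added into one buffer, cells from the other nostril into a second buffer". The other 4 participants are scraped with both methods, one per nostril, and their samples go to histology.

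Protocol 7.2.8.8 makes quantity and quality two separate measurements. Quantity is read on a Nanodrop. Quality is the RIN from an instrument that "delivers a mark from 1 to 10 (10 is the best".

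Protocol 12.1 then plans: "RNA concentration will be summarized by method using descriptive statistics", and "RNA RIN will be summarized by method using descriptive statistics". Both lists include a 95% CI for each method. Protocol 12.1.2 adds: "However, 95% CI will accompany all effect estimates". No method effect is defined for that sentence to apply to.

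SAP 5.5.4.1 summarises RNA by smoking group, and its list of statistics has no CI. SAP Table A 9 is laid out by method, with blocks such as "Only method 1 (5 subjects) RNA". It does not say whether the value is concentration or RIN.

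**The concern.** The stated purpose is to choose between two methods, yet the quantity that bears on the choice, the difference between them, is never estimated. The reader would have to compare two separate summaries of 5 participants each. In the SAP's version, the reader could not even tell which measure is being summarised.

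Two things are hidden as a result. One is how far the observed ranking could be due to chance. The other is whether quantity and quality favour the same method. If they do not, no document in this file says which one decides, so that decision would be taken after the data are seen. The chosen method goes on into later work, so the report should show how firm the choice is.

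**Working it through.** **The plan's own figures.** No sample-size, power or precision figure is given for RNA, so there is none to reproduce. The only sizing statement (protocol 12.2, SAP 5.1) concerns STT: SD 2.5 min, difference 3.75 min, 7 per group. There, 3.75 / (2.5 × √(2/7)) = 2.81, and 2.81 − 1.96 = 0.85, which gives 80.1% power by the normal approximation (73.1% with the t-test). It does not carry over to RNA at 5 per method.

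**The three descriptions side by side.**

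| | Protocol 12.1 | SAP 5.5.4.1 | SAP Table A 9 |
|---|---|---|---|
| Grouping | by method | by smoking group | by method, in a single Total column |
| Concentration and RIN separate | yes | not stated | no |
| Buffers separate | not stated | not stated | no |
| 95% CI per group | yes | no | no |
| Difference between methods | no | no | no |

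Table A 9 also has an RNA block for the 4 participants whose samples the protocol sends to histology. SAP section 6, which lists clarifications to the protocol, does not mention a change of grouping. None of SAP Listings 1 to 15 covers RNA values.

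**Assumptions for the arithmetic.** 5 independent participants per method; one value per participant and measure (the two buffers averaged); equal SDs; normal data. Effects are in SD units because the documents give no SD for RNA. The correlation ρ between concentration and RIN is not given either, so a range is shown.

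**Precision of a method difference.** Half-width = t(0.975, 8 df) × √(2/5) = 2.306 × 0.632 = **1.46 SD**. Each method's own 95% CI has half-width t(0.975, 4 df) / √5 = 2.776 / 2.236 = 1.24 SD. Two such intervals side by side do not give the interval for the difference.

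**If one method is truly better by 0.5 SD on both measures.** On one measure, P(better method has the higher mean) = Φ(0.5 / √(2/5)) = Φ(0.79) = 0.785. For two measures with ρ = 0:

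- better method leads on both: 0.785² = 0.617
- worse method leads on both: 0.215² = 0.046
- measures split: 1 − 0.617 − 0.046 = 0.337

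Other correlations come from the bivariate normal distribution:

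| ρ | better leads on both | worse leads on both | split |
|---|---|---|---|
| −0.5 | 58.2% | 1.1% | 40.8% |
| 0 | 61.7% | 4.6% | 33.7% |
| 0.5 | 66.7% | 9.6% | 23.6% |
| 0.8 | 71.1% | 14.1% | 14.8% |

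With a true advantage of 1 SD on both, the better method leads on both in 88.9% (ρ = 0) to 90.1% (ρ = 0.5).

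**If the methods are identical.** P(the same method leads on both) = 1/2 + arcsin(ρ)/π. This is 33.3% at ρ = −0.5, 40.3% at −0.3, 50.0% at 0 and 66.7% at 0.5. The formula contains no n. Simulation with 5 per method agrees. With lognormal concentration and RIN rounded to 0.1, comparing means gives 49.6% at ρ = 0 and 64.1% at ρ = 0.5.

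**The case against.** The study is declared exploratory, with no hypotheses and no formal powering. The phrase about the optimal method is an aim in background and rationale text. Nowhere is it written that the higher of two sample means wins. The same objective also has a histology part, reported separately. Selection criteria might stand in the separate Rhino-probe procedure document or in the sponsor's laboratory SOPs, neither of which is in this file. Protocol 12.1 does plan an SD and a 95% CI per method for each measure, so uncertainty is not wholly absent. If two methods are identical, carrying either forward costs little.

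Most of this stands, and it limits the point. A reader might infer that the plan has a built-in rule that declares a winner at least half the time when the methods do not differ. The documents do not support that. They state no such rule, and they give no correlation between concentration and RIN. The figure falls below one half as soon as that correlation is negative. It also does not depend on the number of participants, so it is not a consequence of 5 versus 5.

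What the objection does not answer is the missing estimate. Being exploratory excuses low power, but it does not explain why the difference of interest goes unreported. The protocol's per-method intervals are dropped in the SAP, whose table also leaves the measure unnamed.

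**Conclusion.** The point holds as a gap in the planned output. The aim is to choose a method on RNA quantity and quality from 5 versus 5 participants. No between-method estimate is planned in either document, and the SAP output as written cannot show which method leads on which measure.

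The uncertainty left unshown is large: a 95% CI half-width of about 1.46 SD for the difference. With a true 0.5-SD advantage on both measures and a correlation of 0 to 0.5, ranking the means puts the better method ahead on both in about 62-67% of trials. The rest are split (24-34%) or wrong (5-10%). With identical methods, one leads on both in half of trials or more only if the two measures are not negatively correlated.

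These figures rest on the assumed normality, equal SDs and correlation, and on reading the choice as a comparison of means. The gap in the output does not depend on them. This is a minor, nearly free improvement, and it does not touch the primary objectives.

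**What to change.** In SAP 5.5.4.1 and Table A 9:

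- Report RNA concentration and RIN in separate blocks by method, with the 95% CIs of protocol 12.1. Reconcile the smoking-group wording and the RNA block for the 4 histology participants with the protocol.
- Add the method 1 minus method 2 difference in RIN, and the ratio of geometric means (method 1 to method 2) for concentration, each with a 95% CI.
- Take the participant as the unit (5 per method) and buffer as a within-participant factor, so that the 10 samples per method are not counted as 10 independent observations.
- Name in advance which measure leads if the two disagree. If the procedure document or a laboratory SOP already settles this, cite it.
- Describe the chosen method as provisional in light of the intervals.

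I would not add a significance criterion for calling a method optimal. At 5 versus 5, a two-sided 5% comparison has about 29% power for a 1-SD difference and reaches 80% only near 2.0 SD. It would rarely separate the methods, and it does not suit a study without hypotheses.

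The cost is SAP wording and a few table rows, with no new samples or participants. The downside is that the wide intervals will often show that neither method is clearly better.
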